### **11.3. Adverse Events**

All adverse events will be coded using MedDRA version 23.1. AE monitoring will begin from the signature of the Informed Consent Form (ICF) until the 6 month Post Treatment Follow-up Visit. SAE monitoring will begin from the signature of the ICF until the 6 month Post Treatment Follow-up Visit.

Adverse events with an onset date strictly prior to the first MTX treatment in the MTX Tolerability Assessment Period will be called non-treatment-emergent events.

Treatment-emergent AEs (TEAEs) for the MTX Tolerability Assessment Period are defined as events with an onset date on or after the first dose of MTX (but not on or after the first MTX or placebo date in subjects who entered the Run-in Period) through 30 days after the last dose of MTX for subjects who did not receive MTX or placebo in Run-in Period.

Treatment-emergent AEs (TEAEs) for the Run-in period are defined as events with an onset date and time on or after the first dose of MTX or placebo in the Run-in Period (but not on or after the first infusion date of pegloticase in subjects who entered the Pegloticase + IMM Period) through 30 days after the last dose of MTX or placebo for subjects who did not receive pegloticase.

TEAEs for the Pegloticase + IMM Period are defined as events that occur on or after the start date and time of the first pegloticase infusion through 30 days after the last dose of pegloticase and/or MTX or placebo (whichever is later).

Adverse events with an onset date more than 30 days after the last dose of pegloticase and/or MTX or placebo (whichever is later), will be adverse events in the follow-up period.

All AEs, both serious and non-serious, will be assessed for severity using the Rheumatology Common Toxicity Criteria (CTC) v2.0. Missing data conventions for AEs are described in Section 6.3.2. The imputed onset dates will be used to determine the period of onset. Summaries of TEAEs in the MTX Tolerability Assessment Period will be provided using the MTX Population. Summaries of TEAEs in the Run-in Period and in the Pegloticase + IMM Period will be provided for the safety population.

An overall summary of TEAEs will be provided for the MTX Tolerability Assessment Period. TEAEs will be presented by treatment group for the Run-in Period and Pegloticase + IMM Period. Summaries will include the number and percentage of subjects with each AE type as well as the number of events for each of the following:

This document is confidential.

- TEAEs
- Serious TEAEs
- TEAEs related to MTX or placebo
- TEAEs related to pegloticase (applicable to Pegloticase + IMM Period only)
- Serious TEAEs related to MTX or placebo
- Serious TEAEs related to pegloticase (applicable to Pegloticase + IMM Period only)
- TEAEs with an Rheumatology CTC Criteria of 3 or higher
- TEAEs leading to permanent withdrawal of MTX or placebo
- TEAEs leading to permanent withdrawal of pegloticase (applicable to Pegloticase + IMM Period only)
- TEAEs related to MTX or placebo leading to permanent withdrawal of MTX or placebo
- TEAEs related to pegloticase leading to permanent withdrawal of pegloticase (applicable to Pegloticase + IMM Period only)
- TEAEs leading to death

For Pegloticase + IMM Period, the number and percentage of subjects as well as the number of events with any infusion reactions including/excluding anaphylaxis will be included in the summary. In addition, the overall summary of TEAEs during the Pegloticase + IMM Period based on subgroup will be provided.

Using the safety population, an overall summary of AEs occurring during the follow-up period (with onset more than 30 days after the last dose of study medication), including the number and percentage of subjects with each AE type as well as the number of events for each of the following:

- AEs
- Serious AEs
- AEs with an Rheumatology CTC Criteria of 3 or higher
- AEs leading to death

Percentages for the overall summary of AEs during follow-up will be based on the number of subjects who had follow-up more than 30 days after last dose of medication.

Additional AE summaries will be provided by onset period, including the number, percentage of subjects, experiencing TEAEs for the following:

This document is confidential.

- TEAEs overall and by SOC and PT for the: MTX Tolerability Assessment Period, Run-in Period, Pegloticase + IMM Period, and Follow-up Period
- TEAEs by maximum severity, overall and by SOC and PT for the MTX Tolerability Assessment Period, Run-in Period, and Pegloticase + IMM Period
- TEAEs related to MTX or placebo overall and by SOC and PT for the MTX Tolerability Assessment Period, Run-in Period, and Pegloticase + IMM Period
- TEAEs related to pegloticase overall and by SOC and PT for the Pegloticase + IMM Period only
- TEAEs Related to MTX or placebo by maximum severity, overall and by SOC and PT for the: MTX Tolerability Assessment Period, Run-in Period, and Pegloticase + IMM Period.
- TEAEs Related to Pegloticase by maximum severity, overall and by SOC and PT for the Pegloticase + IMM Period only
- Serious TEAEs, overall and by SOC and PT for the: MTX Tolerability Assessment Period, Run-in Period, Pegloticase + IMM Period, and Follow-up Period
- TEAEs leading to permanent withdrawal of MTX or placebo, overall and by SOC and PT for the: MTX Tolerability Assessment Period, Run-in Period, and Pegloticase + IMM Period)
- TEAEs leading to permanent withdrawal of pegloticase, overall and by SOC and PT for the Pegloticase + IMM Period only
- COVID-19 Infection TEAEs by maximum severity, overall and by SOC and PT for the: MTX Tolerability Assessment Period, Run-in Period, Pegloticase + IMM Period, and Follow-up Period

In addition, the summary of TEAEs by SOC and PT during the Pegloticase + IMM Period based on subgroup will be provided. Also, AEs that occur after the start of commercial pegloticase will be summarized by SOC and PT and relationship to commercial pegloticase for subjects who take commercial pegloticase after discontinuation of study pegloticase. Similarly, AEs that occur after the start of commercial MTX will be summarized by SOC and PT and relationship to commercial MTX for subjects who take commercial pegloticase after discontinuation of study MTX. The tables summarizing commercial product use will only be created if at least 25 subjects take commercial product.

The incidence per person years of exposure to MTX or placebo and incidence per person years of exposure to pegloticase will be provided on all tables except those summarizing events by maximum intensity, and those for the post-treatment follow-up period. The person years (PY) of exposure is defined as  $[(\text{last treatment date in the period} - \text{first treatment date in the period} + 1)/365.25]$ . Total PY of exposure to pegloticase will be calculated separately for each treatment arm.

For summaries by SOC, PT, and maximum severity, a subject will only be counted once for each SOC based on the maximum intensity level reported for that SOC and once for each unique PT

This document is confidential.

within that SOC level at the maximum intensity level reported for that PT. For summaries by SOC and PT only, a subject will be counted at most once at the SOC level and at most once at each unique PT within the SOC level. Summaries presenting the frequency of TEAEs by SOC and PT will be ordered alphabetically by SOC and then, within a SOC, alphabetically by PT.

In addition to the listing of all AEs, separate listings will be provided for serious AEs, AEs leading to withdrawal of MTX or placebo, AEs leading to withdrawal of pegloticase, AEs leading to study discontinuation, AEs of special interest, COVID-19 AEs, AEs occurring while taking commercial pegloticase and/or MTX, adjudicated AEs, and AEs leading to death. TEAEs and the period of onset will be identified on each listing.

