- Fill gout prophylaxis, fexofenadine, acetaminophen, and folic acid prescriptions, as needed.
- Administer MTX/placebo for MTX  $\geq$ 60 minutes prior to pegloticase infusion if subject has not taken MTX/placebo for MTX within the previous 1 to 3 days.

- Obtain blood samples for MTX Polyglutamate analysis prior to the infusion.
- Obtain blood samples for anti-PEG and anti-uricase IgG antibodies prior to the infusion.
- Obtain optional whole blood and serum samples from subjects who consent for future analysis.
- Administer IR prophylaxis (i.e., fexofenadine, acetaminophen, and methylprednisolone) (see Section 9.4.1.3).
- Administer the first dose of pegloticase and record date, volume, and duration of infusion, and start/stop (inclusive of 10-mL flush) times of dosing.
- Obtain blood samples for pegloticase PK analysis any time after the end of the infusion, prior to discharge from the site.
- Obtain 1 blood sample for measurement of sUA after the end of the pegloticase infusion for shipment to the Central Laboratory.
- Obtain blood and urine samples for allantoin any time after the end of the infusion, prior to discharge from the site.
- Inquire about AEs and concomitant medication use.

### 9.5.8.2.2 Week 2

- Obtain 2 blood samples for measurement of sUA within 48 hours prior to the pegloticase infusion at this visit. One sample will be tested for sUA at the site's Local Laboratory and one sample will be shipped to the Central Laboratory for testing. The Local Laboratory or Central Laboratory pre-infusion sUA results should be reported prior to pegloticase infusion. To note: It is allowable for the Local and Central Laboratory sUA samples to be drawn on different days or times so long as both samples are drawn within 48 hours prior to the infusion and the results of at least one sample are available prior to the infusion. (see Section 9.5.1.1).
- Administer MTX/placebo for MTX  $\geq$ 60 minutes prior to pegloticase infusion if subject has not taken MTX within the previous 1 to 3 days.
- Document gout flares and intensity.
- Record vital signs (blood pressure, respiratory rate, temperature, and heart rate) prior to the pegloticase infusion and any time after the end of the infusion, but prior to discharge. (see Section 9.5.4.4).
- Assess MTX/placebo for MTX compliance and re-dispense MTX/placebo for MTX.

- Ask Yes/No question regarding folic acid, gout flare prophylaxis, and IR prophylaxis compliance.

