### 9.6.7 Safety Analysis

Treatment-emergent AEs (TEAEs) during the MTX Tolerability Assessment Period and Run-In Period are defined as events with an onset date on or after the first dose of MTX through the first pegloticase infusion, or 30 days after the last dose of MTX for subjects who do not receive pegloticase. TEAEs during the Pegloticase + IMM Period are defined as events that occur after the start of the first pegloticase infusion through 30 days after the last dose of pegloticase and/or MTX or placebo for MTX (whichever is later). TEAEs that occur during the MTX Tolerability Assessment Period prior to randomization (Weeks -6 to -4) will be summarized separately for the MTX population. TEAEs will be summarized for the safety population separately for the Run-In Period (after randomization at Week -4 to Day 1) by treatment group (MTX and placebo for MTX) and the Pegloticase + IMM Period by treatment group (pegloticase with MTX and pegloticase with placebo for MTX), and overall (after randomization through 30 days after the last dose of treatment) by treatment group (MTX and placebo for MTX). AEs that occur more than 30 days after the last dose of pegloticase and/or MTX or placebo for MTX through the 6 month follow-up visit will also be summarized.

The number and percentage of subjects experiencing AEs will be summarized by system organ class and preferred term. Summaries by maximum severity and relationship to MTX and/or pegloticase will also be provided. SAEs and AEs leading to discontinuation of MTX and/or pegloticase will be presented by system organ class and preferred term.

The proportion of subjects with SAEs and each AESI will be summarized by treatment group. A Fisher's exact test will be performed to evaluate the difference in proportions between pegloticase with MTX vs. pegloticase with placebo for MTX. The proportion of subjects experiencing an SAE and each AESI will be summarized for each treatment group, along with the treatment difference in proportions, corresponding 95% CI for the treatment difference and p-value.

Laboratory test results, including urine albumin:creatinine ratio, will be summarized by study visit and change from baseline. Shift tables for laboratory parameters by Common Terminology Criteria for Adverse Events grade will be presented. Laboratory test results will also be classified relative to the normal reference range (normal, low, or high).

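### SAP 11.3 closes two adverse-event windows on a calendar date but opens the next at a clock time, so a timed event earlier on the boundary day falls in no treatment-emergent period

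*SAP*

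**What the plan says.** SAP 11.3 sorts adverse events by onset into five categories.

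- **Non-treatment-emergent:** "Adverse events with an onset date strictly prior to the first MTX treatment in the MTX Tolerability Assessment Period will be called non-treatment-emergent events".
- **Tolerability:** from the first open-label MTX dose, "but not on or after the first MTX or placebo date in subjects who entered the Run-in Period".
- **Run-in:** the opening bound is "events with an onset date and time on or after the first dose of MTX or placebo in the Run-in Period". The closing bound, for anyone who goes on to be infused, is set by calendar day: "but not on or after the first infusion date of pegloticase in subjects who entered the Pegloticase + IMM Period".
- **Pegloticase + IMM:** "events that occur on or after the start date and time of the first pegloticase infusion". This window then stays open until 30 days past the final dose.
- **Follow-up:** "Adverse events with an onset date more than 30 days after the last dose of pegloticase and/or MTX or placebo".

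The TEAE tables are built by period from these definitions. Protocol 9.6.7 draws the line differently. Its pre-pegloticase window covers "events with an onset date on or after the first dose of MTX through the first pegloticase infusion", it separates Tolerability from Run-in at randomization, and it adds an overall post-randomization summary by arm. SAP 11.3 defines no such combined window.

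**The concern.** At each of the two internal boundaries the earlier window stops at midnight at the start of the boundary day, while the later one waits for the dose or infusion. The hours in between are on treatment but unassigned, and a programmer who follows the text exactly will leave an event in them out of every period-based TEAE table.

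These hours are not idle on Day 1. Before the first infusion the protocol provides for blinded MTX or placebo if it was not taken in the preceding days, oral and intravenous infusion-reaction prophylaxis, a targeted physical examination, and hematology and chemistry sampling. Clinically significant findings from that examination are recorded as adverse events. Findings dated to the visit would bear on Run-in safety, which is tabulated by randomized arm.

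**Working it through.** The plan states no figure that depends on this point, so the check sets the definitions side by side.

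**Step 1. Bounds as written in SAP 11.3**

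| Boundary | Earlier window ends | Later window starts |
|---|---|---|
| First open-label MTX dose | before the date | on the date |
| First blinded dose | before the date | at the date and time |
| First infusion | before the date | at the start date and time |

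The first row is consistent. The other two leave a gap from midnight to the dose or infusion. They apply only to subjects who go on to the next period, because the date exclusions are limited to those subjects.

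**Step 2. Does another rule close the gap?** The non-treatment-emergent category ends at the first open-label dose and Follow-up starts more than 30 days after the last dose, so neither reaches these hours. The imputation rules in SAP 6.3.2 deal with incomplete dates. They do not cover a complete date that falls in the gap, or a complete date with no onset time.

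**Step 3. Illustrative timeline.** Clock times are assumed: first blinded dose at 18:00, first infusion at 11:00. Every minute was classified under the literal rules.

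- First blinded-dose day: 18 × 60 = 1,080 minutes unassigned.
- Day 1: 11 × 60 = 660 minutes unassigned.
- No minute was assigned twice.
- On Day 1, an event at 08:00 or 10:59 has no period and one at 11:00 is Pegloticase + IMM. An event at noon the day before is Run-in.

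With one date-and-time cut-point at each boundary, the unassigned time is 0 and nothing is double-assigned. The 08:00 and 10:59 events become Run-in.

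**Step 4. Illustrative size.** The 145 subjects are the planned total in SAP 3.6. The event rate and the half-day gap are assumptions; the documents give neither.

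Expected events per boundary = subjects × uncovered days ÷ 365.25 × events per subject-year.

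145 × 0.5 ÷ 365.25 = 0.1985 subject-years uncovered.

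| Assumed events per subject-year | Events per boundary |
|---|---|
| 5 | 0.99 |
| 10 | 1.98 |
| 20 | 3.97 |

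For Day 1, 145 is an upper limit, since not every randomized subject need receive pegloticase.

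**The case against.** The literal mismatch is hard to dispute. The stronger objections concern what follows from it, and most of them stand.

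- **Events of special interest.** A reader might infer that Day 1 gout flares and premedication reactions vanish from these counts. The documents do not support that. SAP 11.3.1 also tabulates flares from Day 1 to Week 12 by onset date, so a Day 1 flare may still be counted. Infusion reactions are defined as occurring during or after the infusion and are summarized only in Pegloticase + IMM. The cardiovascular summary by period is the one without such a backstop.
- **The main safety comparison.** A reader might infer that the comparison of pegloticase plus MTX with pegloticase plus placebo is distorted. For timed events it is not: once corrected, they go to Run-in or Tolerability. Tolerability is a single MTX column, so only the Run-in tables by arm can change.
- **Visibility.** All adverse events are listed, with period of onset identified, so an unassigned event can be seen there. Subject-level tables count each subject once per term, so a lost event need not change a subject count.
- **Onset times.** An event is shown to lie in the gap only if it has a clock time. The protocol's minimum source record for adverse events (Section 10) names start and stop dates, and the SAP's infusion-reaction summary allows for missing timing. This limits the certain loss but exposes a second hole: an untimed Day 1 event is barred from Run-in by date and cannot be shown to meet the Pegloticase + IMM start.
- **Intent.** SAP Section 12 declares no changes from the protocol, only details and clarifications. This looks like loose drafting, not a chosen departure. The protocol's own Day 1 wording is not clean either: its two windows overlap during the first infusion. An overlap does not lose events, however.

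**Conclusion.** The point holds as an error in the definitions with limited consequences. SAP 11.3, followed exactly, leaves timed adverse events on two part-days per subject in no treatment-emergent period. They are absent from the period-based TEAE and serious TEAE tables and from the by-period cardiovascular summary, though not from the listings.

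The count affected is likely small and cannot be derived from the documents. The 1 to 4 events per boundary rest wholly on an assumed 5 to 20 events per subject-year, half a day uncovered and all 145 subjects crossing. They are events of any grade, and there is no basis for a separate serious-event figure. Adding the two boundaries (about 2 to 8) would overstate the effect on comparisons between arms, because only the Day 1 boundary feeds a by-arm table that the correction changes for events that are now lost. Onset dates may cluster on visit days, but the documents give nothing with which to size that.

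**What to change.** In SAP 11.3:

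1. Close the Tolerability window immediately before the date and time of the first blinded dose, for subjects who take one.
2. Close the Run-in window immediately before the date and time at which the first infusion begins, for subjects who receive one.
3. Add a rule that an event dated to a boundary day with no onset time is assigned to the later period. This is in line with SAP 6.3.2, which imputes the first infusion date and classes the event as Pegloticase + IMM when only the infusion shares the onset month.

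The third rule can add untimed Day 1 events to Pegloticase + IMM, so it should be settled before unblinding. The cost is a few phrases in one section and the matching derivation code. No data collection, visit or treatment changes.

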Vital signs, including blood pressure, respiratory rate, temperature, and heart rate, will be summarized by study visit and change from baseline.

Prior and concomitant medications will be summarized and/or included in the data listings.

Data for the MTX Tolerability Assessment Period, Run-in Period and Pegloticase + IMM Period will be summarized separately, and for the Run-in and Pegloticase + IMM periods combined, where applicable.

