## **11. Safety**

Safety analyses will be based on the safety population and the MTX population, depending on the treatment period. The MTX population will be used for analysis of safety data during the MTX Tolerability period prior to randomization and the safety population will be used for analysis thereafter. For summaries by study period, the number of subjects included in the Safety Population for each period will be the number of subjects with data in that period (e.g. for the Pegloticase + IMM Period, subjects must have received pegloticase).

Safety will be assessed via AEs including AEs of special interest (AESI [i.e., IRs, anaphylaxis, gout flares, and cardiovascular events]), concomitant medication use (refer to Section 8.3), physical examinations, vital signs, clinical safety laboratory evaluations (complete blood count, chemistry, urine albumin:creatinine ratio), pregnancy testing (if applicable), and electrocardiograms (ECGs).

All safety information will be provided in subject listings.

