## **12. Changes from Analysis Planned in Protocol**

In those cases in which this SAP details changes from the analyses specified by the protocol, the analyses specified in this SAP will supersede those in the protocol. There are no changes from Amendment 3 of the protocol but details and clarifications are described in this SAP.

This document is confidential.

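### The readable SAP tabulates adverse events only by separate period and omits the protocol's combined post-randomisation TEAE summary by arm

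*SAP*

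**What the plan says.** Protocol 9.6.7 plans TEAE summaries for the safety population in three ways: for the Run-in by arm, for the Pegloticase + IMM Period by arm, "and overall (after randomization through 30 days after the last dose of treatment) by treatment group (MTX and placebo for MTX"). The section's last paragraph repeats the commitment: data are shown separately by period "and for the Run-in and Pegloticase + IMM periods combined, where applicable".

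The SAP is built on periods:

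- **Overview table (SAP 11.3).** "TEAEs will be presented by treatment group for the Run-in Period and Pegloticase + IMM Period".
- **All further AE tables (SAP 11.3).** "Additional AE summaries will be provided by onset period". This covers system organ class and preferred term, severity, relatedness, serious events and withdrawals.
- **Run-in window (SAP 11.3).** It opens at the first blinded dose and excludes later events: "but not on or after the first infusion date of pegloticase in subjects who entered the Pegloticase + IMM Period". For subjects never infused it runs to 30 days after the last blinded dose.
- **Denominators (SAP 11).** Each period counts only subjects with data in it: "for the Pegloticase + IMM Period, subjects must have received pegloticase".
- **Columns (SAP 6.1).** Layouts are given for single periods only.
- **Declared changes (SAP 12).** "There are no changes from Amendment 3 of the protocol". The protocol supplied is Version 3.0, Amendment 2, Administrative Change 1.

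**The concern.** MTX against placebo is the only randomised difference in this trial, and blinded dosing starts four weeks before the first infusion. The safety comparison that randomisation supports therefore runs from the first blinded dose. Splitting it at the first infusion gives one table that stops at that point and a second restricted to subjects who reached it, which is a selection made after randomisation. The protocol's combined summary puts the comparison back together.

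Without it, the study report could not state what proportion of each randomised arm had a TEAE, an SAE, or an AE that ended MTX or placebo during blinded treatment. In a trial asking whether adding MTX is worthwhile, that is a basic safety figure.

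**Working it through.** The plan states no figure to reproduce here; the check is a comparison of texts, followed by an illustration with assumed counts.

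**1. The texts side by side**

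| Summary by arm | Protocol 9.6.7 | Readable SAP 6.1, 11, 11.3 |
|---|---|---|
| Run-in | yes | yes |
| Pegloticase + IMM | yes | yes, infused subjects only |
| Both combined, to 30 days after last dose | yes, stated twice | not described |

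In SAP 11.3 the wording about events overall and by system organ class means any event within a period, not across periods. The SAP does use the longer span elsewhere: SAP 11.1 summarises MTX exposure for the whole study and SAP 11.2 reports compliance from randomisation onward. Adverse events have no counterpart.

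**2. Three kinds of subject in the described tables**

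- *Leaves in the Run-in, never infused.* Counted in the Run-in tables; absent from numerator and denominator of the Pegloticase + IMM tables.
- *Has a Run-in event, later infused.* In the Pegloticase + IMM denominator, but the Run-in event is not counted there. Protocol 9.1 lets subjects intolerant of blinded MTX stay in the study, so this group may be larger than the first.
- *Has events in both periods.* Counted once in each table, with nothing to show the overlap. Under SAP 6.3.2 even one event with a partial onset date can be treated as emergent in both periods.

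**3. Why the tables cannot be added**

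Let R and P be the subjects with an event in the Run-in and Pegloticase + IMM tables, and N the arm's Safety Population. The number with an event at any time lies between max(R, P) and min(N, R + P). SAP 3.6 plans 145 randomised at 2:1: 145 × 2/3 = 96.7 and 145/3 = 48.3, so take 97 and 48. If an MTX-arm SAE table showed R = 5 and P = 10 (assumed), the combined figure could be anything from 10/97 = 10.3% to 15/97 = 15.5%.

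**4. Illustration for AEs leading to MTX/placebo withdrawal**

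Assumptions, none from the documents: 10 MTX and 3 placebo subjects have such an AE in the Pegloticase + IMM Period, and each Run-in leaver had one and was never infused. With L leavers in an arm and E later events, the period table shows E/(N − L) and the combined table (E + L)/N.

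| Leavers, MTX vs placebo | Pegloticase + IMM table | Difference (points) | Combined table | Difference (points) |
|---|---|---|---|---|
| 2 vs 0 | 10/95 = 10.5% vs 3/48 = 6.2% | 4.3 | 12/97 = 12.4% vs 3/48 = 6.2% | 6.1 |
| 5 vs 1 | 10/92 = 10.9% vs 3/47 = 6.4% | 4.5 | 15/97 = 15.5% vs 4/48 = 8.3% | 7.1 |
| 8 vs 1 | 10/89 = 11.2% vs 3/47 = 6.4% | 4.9 | 18/97 = 18.6% vs 4/48 = 8.3% | 10.2 |
| 0 vs 2 (first row mirrored) | 10/97 = 10.3% vs 3/46 = 6.5% | 3.8 | 10/97 = 10.3% vs 5/48 = 10.4% | −0.1 |

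The last row shows that the direction is not fixed by the design.

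**The case against.** The strongest reply is that this is a documentation gap and that no safety information is lost. Much of that stands.

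- Run-in events are reported by arm, including serious events, deaths and permanent withdrawals of MTX or placebo. SAP 7 gives Run-in discontinuations by arm, and SAP 11.3 lists withdrawal AEs. A reader might infer that subjects who leave for MTX toxicity vanish from the between-arm reporting; the documents do not support that. The Run-in table covers every randomised and dosed subject from the first blinded dose.
- A reader might take the Pegloticase + IMM table as the main safety table. The SAP ranks no table.
- A reader might also infer a bias in favour of MTX. That needs Run-in losses that the documents do not give. Everyone randomised had tolerated two weeks of MTX 15 mg, and intolerance after randomisation does not force a subject out.
- Permanent withdrawal should happen once per subject, so for that outcome a reader could add the two counts and divide by the Safety Population. This does not work for TEAEs or SAEs.
- The SAP's index of tables is redacted and the Amendment 3 it cites was not supplied, so a combined table listed there cannot be excluded. SAP 12 lets the SAP supersede the protocol where it details a change; silence is arguably not such a change, and the protocol's second statement is qualified by applicability.

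None of this supplies the missing comparison. The readable AE section is detailed and contains no combined period.

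**Conclusion.** The point holds as a mismatch between protocol and SAP with a practical consequence. On the readable text, a programmer following the SAP would produce no single by-arm comparison of TEAEs, SAEs or MTX/placebo-withdrawal AEs over blinded treatment, although the protocol asks for the combined TEAE summary and SAP 12 declares no departure. For TEAEs and SAEs the gap cannot be closed from the period tables, because subjects with events in both periods cannot be de-duplicated.

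The size is unknown. The illustrated shifts (for example 4.5 to 7.1 points with 5 vs 1 leavers) rest wholly on assumed counts, and the sign depends on which arm loses subjects or has events in the Run-in. The conclusion also assumes that no combined table sits in the redacted index. It does not touch the efficacy analysis.

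**What to change.** In SAP 11.3, add the protocol's combined period: onset on or after the first blinded MTX/placebo dose, to 30 days after the last dose of any study drug, by arm, with the whole Safety Population as denominator. Starting at the first blinded dose matches how that population is defined. Produce the TEAE, SAE and MTX/placebo-withdrawal AE tables on it, and the gout flare and cardiovascular event summaries, alongside the period tables. Keep infusion reactions and anaphylaxis on infused subjects, since these are summarised for the Pegloticase + IMM Period only. Making the combined table the primary safety display would be a preference; the protocol sets no such order.

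If the omission is deliberate, state and justify it in SAP 12 and correct or explain the amendment number there. At the same time, clarify the gout flare denominator in SAP 11.3.1, which names the safety population for the full Pegloticase + IMM Period, against the rule in SAP 11 that limits that period to infused subjects.

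The cost is SAP wording and a few extra tables from existing data. No protocol amendment is needed, because the supplied protocol already contains the commitment.
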